8.2. Screening and Eligibility Assessment

After consent to take part has been given the following information will be collected about each patient and recorded on the CRFs:

- Demographics
 - Date of birth, gender, BMI, height, weight, and smoking status
- Medical history
 - Details of history of disease or surgical intervention in the following systems: inflammatory joint disease, previous surgery, previous joint infections, contralateral hip disease
- Concomitant medication
 - All over the counter or prescription medication

The maximum time between screening and randomisation is one year.

8.3. Informed Consent

The participant must personally sign and date the latest approved version of the Informed Consent form before any trial specific procedures are performed.

Written and verbal versions of the Participant Information and Informed Consent will be presented to the participants detailing no less than: the exact nature of the trial; what it will involve for the participant; the implications and constraints of the protocol; the known side effects and any risks involved in taking part. It will be clearly stated that the participant is free to withdraw from the trial at any time for any reason without prejudice to future care, without affecting their legal rights and with no obligation to give the reason for withdrawal.

The participant will be allowed as much time as wished to consider the information, and the opportunity to question the Investigator, their GP or other independent parties to decide whether they will participate in the trial. Written Informed Consent will then be obtained by means of participant dated signature and dated signature of the person who presented and obtained the Informed Consent. The person who obtained the consent must be suitably qualified and experienced, and have been authorised to do so by the Chief/Principal Investigator. A copy of the signed Informed Consent will be given to the participant. The original signed form will be retained at the study site.

8.4. Randomisation, blinding and code-breaking

Following written informed consent and confirmation of eligibility, all patients will be randomised into the study. Patients will be allocated a study number and will be randomised on a 1:1 basis to receive one of the two treatment options. During study recruitment, 50 participants (25 in each study arm) will be randomly selected to undergo gait analysis. At the end of study recruitment, 50 participants will be randomly selected from arm 2 (OPS arm) of the study cohort to have a second CT scan, which will be performed at 12-months post-operatively.

Randomisation will be performed using an automated computer-generated minimisation system through the Oxford Surgical Interventional Trials Unit to age (<40, ≥40 and <65, or ≥65), and gender. This process will occur centrally in Oxford and be overseen by the trial coordinator. Investigators at other sites will contact the site in Oxford to get each participant's randomisation allocation. Patients will be blinded as to which arm of the trial they have been allocated. The Oxford trial coordinator, the operating surgeon and the theatre staff will be unblinded and aware of which treatment arm the patient is in. The post-operative care team will remain blinded.

The Oxford trial coordinator will retain a full list of all recruited patients, their anonymous code number, and the treatment arm they have been allocated to. Trial coordinators at other sites and all operating surgeons will have access to a partial list, containing the same information on patients recruited at their own site only.

They will be the only people with access to this list. They will not have any role in collecting, reviewing, or interpreting post-operative data. Members of the research team who will be post-operatively assessing patients clinically, reviewing images or collecting and interpreting PROMs data will be blinded to patient allocation.

We do not anticipate a situation where code breaking will be required because the surgeons are not blinded to which arm the patients are in.

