6. TRIAL DESIGN

This will be a multi-centre, two-arm, single blind (participant blind), randomised controlled group superiority study. It will take place in the NHS hospital setting. Stratification will be performed for age and sex by means of a minimisation technique during randomisation for each subject entering the trial. There will be no limit on the number of sites and no limit on the number of recruits per site. The study site shall maintain a list of the participating sites and investigators separately to the protocol.

Arm 1

Best practice total hip arthroplasty with conventional templating

Arm 2

10/11/17

Protocol 1.2

Page 9 of 28

Does the Corin Optimised Positioning System improve clinical outcome in total hip replacement?

Chief Investigator: [name]

IRAS Project Number: 216084

Rec Reference Number: 17/SC/0506

Best practice total hip arthroplasty with Corin Optimised Positioning System to guide templating

In the study 230 participants will receive best practice THA with conventional templating; the other 230 will receive best practice THA with Corin OPS to guide templating. Any participant that withdraws from the study will not be replaced.

Initially we will perform an internal pilot study of 100 participants, with 50 participants in each arm. This will enable us to check feasibility of recruitment and to check our power calculation is correct. We anticipate recruitment to the pilot study will take six months, with an average of four participants recruited per week. Together the five centres currently recruited performed 3419 primary total hip replacements in 2015, an average of 66 per week⁸. Since participants in the two arms receive the same procedure, with the difference being in the technique used, with clear explanation of the trial to potential participants, we anticipate that approximately 50% of eligible patients that are approached will consent to take part in the trial. With this knowledge, we believe recruitment of initially four (rising to six) participants per week will be attainable. If the internal pilot study shows that completing the study is unfeasible, then the trial will be terminated following mutual agreement from both the Chief Investigator and the funder (Corin Limited). We anticipate recruitment to the full trial will take two years.

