The expected duration of participant participation is 15 months. Following recruitment in outpatient clinics, participants will undergo baseline assessments, including imaging (CT scan and x-rays of pelvis) and clinical assessment. A subset of 50 participants will be randomly selected to also undergo gait analysis as part of the baseline assessments pre-operatively. All participants will then undergo THA surgery, which will likely entail an in-patient hospital stay of 1-7 days. Post-operative rehabilitation will be in line with the normal standard care for all participants. Post-operatively participants will make three additional visits to clinic at 3, 6 and 12 months, compared to routine follow up. At every visit, participants will complete the PROM questionnaires and undergo clinical assessment, as specified in section 5. Any dislocations or further surgeries will be recorded. All healthcare visits will be recorded, to enable cost analysis. At the 12 month post-operative visit participants will have standardised anteroposterior and lateral X-rays taken. At the 12-month visit, the subset of participants who were selected to undergo gait analysis pre-operatively will undergo repeat gait analysis. The subset of 50 patients who were randomly selected to undergo a second pelvic CT scan, will have this scan performed at the 12-month visit. Any patients in the study who do suffer a dislocation will be managed in line with the normal standard care. See sections 8.5 and 8.6 for more detail on visit schedule.

There will also be a third observational arm to the study. When patients are approached in clinic and offered entry into the randomised controlled trial, some patients may decline to take part. These patients will then be offered entry into the third observational arm of the study. This third study arm therefore will consist solely of patients who were approached in clinic but declined to be randomised into the clinical trial.

Patients in the third observational arm will continue in routine care as normal, and will not make any additional study visits. Their demographics will be collected and their pre- and post-operative Oxford hip scores and EQ-5D scores will be collected, as occurs in routine care. This third observational study arm will enable an assessment of whether the cohort who consented to undergo randomisation and enter the two randomised study arms are representative of all patients.

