8.6. Summary of Visits

Routine clinical practice will take priority and the study timetable has been drawn up to allow the study procedures to fall within current surgical waiting times. Taking part in the study, therefore, will not delay or expedite treatment. Below is a summary of what will take place at each visit:

Visit 1: Consent visit

- Scheduled within 4-6 weeks of when potential participants are initially approached
- Consent form discussed and signed
- Following this visit, participants will be randomised into one of the two study arms
- If patients decline entry into the study, they will be offered entry into the 3rd observational arm of the study

Visit 2: Baseline assessment visit

- Scheduled for soon after consent visit
- Baseline assessments (detailed in section 8.5) completed

Visit 3: Gait Analysis Visit (subset of patients only)

- Scheduled for same day as or soon after baseline assessment visit (because scheduling CT scan and gait analysis on the same day may not be possible)

Visit 4: Study intervention

- Scheduled for 6-8 weeks after the baseline assessment (Thus patients will have a wait for surgery of approximately 3 months after entry into the study, which is in line with the current surgery waiting time in the participating centres.) Participants will undergo THA surgery in accordance with their randomisation allocation.
- Operative details to be collected:

- Date of surgery
- Randomisation group
- Name of consultant in charge of care
- Grade of lead surgeon
- Grade of assistant surgeons
- Operative side
- Duration of surgery
- Estimated blood loss
- Surgical approach
- ASA grade
- Use of systemic prophylactic therapy (antibacterial and anticoagulant)
- Anaesthesia type
- Acetabular and femoral bone quality
- Whether there was an attempt to correct leg length (if so, what amount attempted and achieved)
- Occurrence of per-operative complications
- Ease of reduction
- Acetabular grafting performed
- Femoral grafting performed
- Details of hip prosthetic components used – including information from device labels
- Other comments on operation

Visit 5: 3-month post-operative visit

- Completion of PROM questionnaires
- Clinical assessment (to include full examination of hip joint and assessment of leg length discrepancy)
- Recording of dislocations, further surgeries or adverse events
- Recording of details of any other healthcare usage by the participants (for cost analysis)

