- Review of medical records and recording of any significant events

Visit 6: 6-month post-operative visit

- Completion of PROM questionnaires
- Clinical assessment (to include full examination of hip joint and assessment of leg length discrepancy)
- Recording of dislocations, further surgeries or adverse events
- Recording of details of any other healthcare usage by the participants (for cost analysis)
- Standardised anteroposterior and lateral x-rays taken
- Review of medical records and recording of any significant events

Visit 7: 12-month post-operative visit

- Completion of PROM questionnaires
- Clinical assessment (to include full examination of hip joint and assessment of leg length discrepancy)
- Recording of dislocations, further surgeries or adverse events
- Recording of details of any other healthcare usage by the participants (for cost analysis)
- Standardised anteroposterior and lateral x-rays taken
- Gait analysis performed on the subset of 50 participants randomly selected pre-operatively

- Subset of 50 participants will undergo a post-operative CT scan. These 50 participants will be randomly selected from arm 2 (OPS arm) of the study cohort.
- Review of medical records and recording of any significant events

Completion of this visit marks the end of trial participation

Reasonable travel expenses to the hospital for the additional appointments for the study purposes will be reimbursed.

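### The 50 OPS patients for the 12-month CT are drawn only when recruitment closes, by which time the earliest OPS patients have already passed their 12-month visit

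*Combined protocol and SAP*

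**What the plan says.** Section 8.4 sets the timing of the draw: "At the end of study recruitment, 50 participants will be randomly selected from arm 2 (OPS arm) of the study cohort". The same sentence puts the second CT at 12 months after surgery. Section 6 says that the chosen patients "will have this scan performed at the 12-month visit", and section 8.6 says of that visit: "Completion of this visit marks the end of trial participation".

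The time from entry to that visit is given twice. Section 6 states: "The expected duration of participant participation is 15 months". Section 8.6 says that "patients will have a wait for surgery of approximately 3 months after entry into the study", and 12 months of follow-up come after the operation.

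On accrual, section 6 states: "We anticipate recruitment to the full trial will take two years". It also says that recruitment of "initially four (rising to six) participants per week will be attainable". The first stage is described as follows: "Initially we will perform an internal pilot study of 100 participants, with 50 participants in each arm"; it is expected to take six months. The synopsis plans a three-year trial period, and section 15.1 describes funding for three years.

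Section 5 describes the CT subgroup as a random selection from the OPS arm, and section 11.1 fixes it at 50 for financial reasons. Only section 8.4 ties the draw to the close of recruitment. The gait subgroup, by contrast, is selected while recruitment is under way (section 8.4).

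**The concern.** If recruitment lasts longer than the interval from entry to the 12-month visit, the two halves of the rule in section 8.4 cannot both be met for the whole OPS arm. A draw made at the close of recruitment comes too late for the first entrants to be scanned on time.

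Two outcomes are possible. A draw from all OPS patients includes some whose scan would be late, after their participation has ended, or would not be done. A draw restricted to patients still ahead of the visit keeps the timing but omits the earliest OPS cases, so it is no longer a random sample of the arm. The available text (the flow chart is not reproduced in it) has no rule for recall, late scans or replacement, and does not say which of the two is intended.

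Secondary objective 4, achieved against planned cup position, rests on these 50 scans alone.

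**Working it through.** **Inputs.** OPS arm 230 of 460, CT subset 50, dropout 10% (section 11.1); wait for surgery about 3 months (section 8.6); visit at 12 months; pilot of 100 in six months, four rising to six per week, recruitment of two years (section 6); three-year trial period (synopsis, section 15.1).

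**The plan's own figures.** 3 + 12 = 15 months, which matches the stated participation; 15 × 52/12 = 65 weeks. The arm size also reproduces: 414/0.9 = 460, or 230 per arm.

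**Is recruitment longer than 65 weeks?** At four per week throughout, 460/4 = 115 weeks. At six per week throughout, 460/6 = 76.7 weeks. Finishing within 65 weeks would need 460/65 = 7.1 per week, above the highest rate stated.

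**Share past the visit at the draw.** This is the share who entered more than 15 months before recruitment closed. The accrual patterns are assumptions.

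- *Four, then six per week.* 100/4 = 25 weeks and 360/6 = 60 weeks, so recruitment closes at week 85. 85 − 65 = 20 weeks; 20 × 4 = 80 of 460 = 17.4%.
- *Close at month 21.* The end of trial is the last patient's 12-month visit (section 9.2), so a three-year period implies closing by 36 − 15 = month 21. Those who entered by month 21 − 15 = 6 are past the visit. With 100 in six months and then 360 in 15, that is 100/460 = 21.7%. With even accrual it is 6/21 = 28.6%.
- *Close at month 24.* Those who entered by month 24 − 15 = 9 are past the visit. With 100 in six months and then 20 per month, that is (100 + 3 × 20)/460 = 34.8%. With even accrual it is 9/24 = 37.5%.

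Expected number among 50 drawn = 50 × share. The 95% range is hypergeometric (50 drawn from 230).

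| Accrual | Past visit, of 230 | Expected in 50 (95% range) | Still ahead | Still ahead × 0.9 | First entrant late by |
|---|---|---|---|---|---|
| 4 then 6 per week, week 85 | 40 (17%) | 8.7 (4 to 13) | 190 | 171 | 20 weeks, 4.6 months |
| Month 21, pilot then steady | 50 (22%) | 10.9 (6 to 16) | 180 | 162 | 6 months |
| Month 21, even | 66 (29%) | 14.3 (9 to 20) | 164 | about 148 | 6 months |
| Month 24, pilot then steady | 80 (35%) | 17.4 (12 to 23) | 150 | 135 | 9 months |
| Month 24, even | 86 (38%) | 18.8 (13 to 25) | 144 | about 130 | 9 months |

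**Sensitivity to the lag (14 and 16 months).** Week 85: 21.2% and 13.6%. Month 21, pilot then steady: 124/460 = 27.0% and 83.3/460 = 18.1%; even: 7/21 = 33.3% and 5/21 = 23.8%. Month 24, pilot then steady: 39.1% and 30.4%; even: 41.7% and 33.3%.

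**Most favourable case.** At six per week throughout with a 16-month lag (69.3 weeks), 76.7 − 69.3 = 7.3 weeks; 7.3 × 6 = 44 of 460 = 9.6%, or 22 of 230. The chance that a random 50 of 230 misses all 22 is about 0.3%.

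**The case against.** The strongest reply is that section 8.4 does not say the draw must cover every OPS patient ever entered. A random draw among those still ahead of the visit fits its words and keeps every scan on schedule. With about 130 to 171 such patients after dropout, 50 scans are available. This stands in part: a reader might infer that the 50 scans cannot be obtained, and the figures show that they can. But the restricted frame omits the earliest OPS cases, which conflicts with the random selection from the OPS arm promised in section 5.

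A second reply is that the two-year figures give too dark a picture. Recruitment of 24 months plus 15 makes 39 months, which does not fit the three-year period. This stands, so the month-21 figures belong beside the two-year ones. A reader might also add the two years to the six-month pilot and infer that about half the arm is past the visit (51%, 118 of 230). That implies 30 + 15 = 45 months, well outside the planned period and funding, and the documents do not support it as a headline. Nor do all 50 pilot OPS patients fall outside a restricted frame on every schedule: at week 85 it is 40 of 50.

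A third reply is that cup position against plan is an operative result, so a later scan or the loss of early cases may not matter. Nothing in the documents shows that position changes between 12 and 21 months or that early OPS cases differ. Equally, nothing shows that they do not. This limits the weight of the point without removing it.

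**Conclusion.** The point holds. The timing in section 8.4 is defeated by the protocol's own timetable at every recruitment rate it states. With a 15-month lag and the accrual patterns assumed above, about 17% of the OPS arm is past the visit at four then six per week, 22% to 29% if recruitment closes at month 21, and 35% to 38% on two years. Among 50 drawn from the arm, that is about 9, 11 to 14, and 17 to 19 patients. The first entrants' scans would be about 5 to 9 months late, if done at all.

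A reader might infer that objective 4 is biased in a known direction, or that the trial's main comparison is weakened. The documents support neither. Objective 4 is a descriptive, single-arm objective, the size and direction of any bias cannot be computed, and the dislocation comparison does not use these scans. The change should be made because it is cheap and because an on-time scan, once missed, cannot be recovered.

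**What to change.** In section 8.4, replace the opening time phrase of the CT sentence with random selection throughout accrual. Use a concealed list, generated centrally in advance and applied to OPS patients in order of surgery. The selection probability is about 50/230 = 21.7%, updated if the sample size is re-estimated after the pilot, with ordered reserves for withdrawals.

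Reveal each patient's selection only after that patient's operation, including for those still awaiting surgery when recruitment closes. Surgeons then cannot know in advance which cups will be measured. Keep the selections from operating surgeons, theatre staff and outcome assessors, and off the partial lists that section 8.4 gives to site coordinators and surgeons.

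Only arm 2 has a second CT, so news of selection can reveal the allocation, and section 11.6 discards data gathered after unblinding. The current plan carries the same risk. Tell patients and booking staff as late as practicable before the 12-month visit. Align section 8.6.

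The number of CTs and the 12-month timing do not change. The cost is minor set-up in the central system and an amendment with the approvals in section 14.3, made before the first OPS patients reach 12 months.

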5. OBJECTIVES AND OUTCOME MEASURES

Objectives	Outcome Measures	Timepoint(s) of evaluation of this outcome measure (if applicable)

Primary Objective
 
To compare the efficacy of the Corin OPS system to guide templating in THA with standard templating in THA in reducing dislocation
	Dislocation rate and re-operation for dislocation rate	Pre-operatively, then at 3,6 and 12 months post-operatively

Secondary Objectives	
1, PROMs:
 
 • Oxford hip score (OHS) • iHOT33 • HAGOS • Pain detect • EQ5D • UCLA 
Harris hip score (HHS)
 
Length of hospital stay
 
Gait analysis
 
2, Measurement of leg lengths
 
3, Cost of inpatient stay for THA and cost of all patient care pertaining to their THA
 
4, Post-operative position of prosthesis measured relative to planned position, based on pre- and post-operative CT scans
 
5, Operation duration
	
1, PROMS and HHS recorded pre-operatively, then at 3, 6 and 12 months post-operatively. Gait analysis pre-operatively and at 12 months post-operatively (25 patients in each arm). Length of hospital stay will be recorded on discharge
 
2, X-rays and leg lengths will be assessed pre-operatively, then at 12 months post-operatively
 
3, Cost calculated 12 months post-operatively
 
4, CT scans pre-operatively and at 12 months post-operatively
 
5, Recorded at end of operation

1, To determine whether the Corin OPS System improves Harris hip score, patient reported outcome measures (PROMs), reduces hospital stay and normalises gait more effectively than conventional surgery
 
2, To determine whether the Corin OPS System improves leg length discrepancy compared to conventional surgery
 
3, To quantify the cost of Corin OPS within the clinical pathway and perform a full health economic analysis following surgery
 
4, To determine the reproducibility of the Corin OPS templating technique at implanting the acetabular cup into the planned position. This will be performed in a subgroup of 50 patients randomly selected from the OPS arm to undergo a post-operative CT scan
 
5, To determine whether the Corin OPS System increases operation duration compared to conventional surgery
		

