8.5. Baseline Assessments

The follow assessments will be carried out at the baseline appointment:

Validated Patient Reported Outcome Measures (PROMs) Questionnaires:

Oxford hip score (OHS); International Hip Outcome Tool-33 (iHOT33); Hip and Groin Outcome Score (HAGOS); Pain Detect score; University of California, Los Angeles (UCLA) Activity Score; EuroQoL-5D score (EQ5D); Harris hip score (HHS)

CT scan:

CT imaging of pelvis

X-Ray:

Dynamic series of x-rays of pelvis and hip

Pregnancy test

Clinical assessment:

Examination of range of movement; examination of fixed flexion deformity; examination of leg length discrepancy

Subset of 50 participants (25 in each arm) will undergo gait analysis. These participants will be randomly selected from each study arm. Participants with comorbidities that significantly affect their gait will be excluded from gait analysis.

Assessors of all imaging, PROMs, and clinical assessment will be blinded to which arm of the trial patients were in.

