11. STATISTICS

11.1. The Number of Participants

The study's aim is to determine whether the Corin OPS system reduces dislocation rate, compared to standard surgical technique and templating. A literature review found that the dislocation rate after THA was 5.0%^{11,17,18}. A clinically significant difference of interest of 4.5% will be used in this study, meaning the required dislocation rate in the OPS group is <0.5%. We performed a power calculation, with α significance of 0.05 and power of 0.8, which gave a required sample size of 414 participants. Accounting for a dropout rate of 10%, this gives a total required sample size of 460, with 230 participants in each arm.

The first 100 participants recruited will be entered into an internal pilot study. The internal pilot study will study the rate of recruitment of participants and analyse whether completion of recruitment of all patients is feasible within our time limits. If the internal pilot study shows that completing the study is unfeasible, then the full trial will be terminated. The internal pilot study will allow calculation of a provisional dislocation rate (the primary outcome) in the control arm of the study. The rationale for this is that the control arm participants may have a different dislocation rate to that found in our literature review. Using the dislocation rate in the internal pilot study and the minimum clinically significant difference of interest, we will re-calculate the sample size required to fully power the full study. We expect, therefore, that the full study sample size may change by 5% either way from our projected sample size of 476 participants. However, if the size of the cohort increases by more than 5% (to above 500) we may need to re-approach the funder to enable us to recruit additional participants.

The subgroup of 50 participants receiving gait analysis pre-operatively and at 12-month post-operatively will include 25 participants from each study arm. The sample size of 50 is of sufficient size to give detailed information. Analysis on a larger group is not possible due to gait laboratory capacity constraints.

The subgroup of participants receiving a 12-month post-operative CT scan will include 50 participants from the OPS arm. The position of the implant compared to the planned position will be analysed. The sample size of 50 is of sufficient size to give detailed information. Analysis on a larger subgroup is not possible due to financial constraints.

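### The OPS-only second CT falls at the 12-month assessment visit and could unblind that assessment for up to 22% of one arm (24% of expected completers) and no controls

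*Combined protocol and SAP*

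**What the plan says.** Section 8.4 provides that, when recruitment ends, "50 participants will be randomly selected from arm 2 (OPS arm) of the study cohort to have a second CT scan". Section 6 says the patients "randomly selected to undergo a second pelvic CT scan, will have this scan performed at the 12-month visit", and section 8.6 lists the scan under Visit 7: "Subset of 50 participants will undergo a post-operative CT scan".

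The same visit carries the last round of outcome assessment. Section 5 has "PROMS and HHS recorded pre-operatively, then at 3, 6 and 12 months post-operatively". Section 6 adds: "At every visit, participants will complete the PROM questionnaires and undergo clinical assessment". Visit 7 in section 8.6 also includes the hip examination, leg-length assessment, x-rays, gait analysis for its own subset, and the recording of dislocations.

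On blinding, section 8.4 says that patients do not know their arm. It says the same of the research staff who examine patients after surgery, review images or handle PROMs. Section 8.5 repeats this: "Assessors of all imaging, PROMs, and clinical assessment will be blinded to which arm of the trial patients were in". That sentence sits under the heading for baseline assessments, so the 8.4 statement is the firmer basis for the 12-month visit.

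Section 11.6 includes every randomised participant, but uses only data collected before unblinding for anyone who becomes unblinded. Section 11.2 calls for intention to treat.

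**The concern.** A procedure given to one arm only is a marker of allocation. The protocol avoids this elsewhere: the pre-operative CT is done in both arms (section 9) and the gait subset is 25 per arm (section 8.4), so neither gives the arm away. The second CT is the exception, and it falls where the final PROMs, Harris hip score, examination and leg-length measures are taken.

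The selection rule is in the protocol that assessors work under. The plan does not say in what order Visit 7 is to run, who books the scan, or that the booking is to be kept from the assessor.

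The exposure is one-sided. Expectation in an assessor or patient who infers OPS could move the OPS mean while the control mean stays put. The outcomes at stake are the 12-month patient-reported and assessor-scored secondary outcomes.

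**Working it through.** **Inputs**
- Second CTs: 50 from the OPS arm, 0 from control (8.4).
- Arm size: "this gives a total required sample size of 460, with 230 participants in each arm" (11.1).
- Dropout 10%, dislocation rates 5.0% and 0.5%, power 0.8 (11.1); two-sided 5% level (11.3).

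**Step 1. Reproduce the plan's denominator.** Two proportions, pooled variance under the null, no continuity correction:

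n per arm = [1.96 × √(2 × 0.0275 × 0.9725) + 0.8416 × √(0.05 × 0.95 + 0.005 × 0.995)]² / 0.045² = 206.1, rounded up to 207.

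Total 2 × 207 = 414, and 414 / 0.9 = 460, or 230 per arm. Both stated figures reproduce.

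**Step 2. Share of the arm exposed**
- Of those randomised: 50 / 230 = 21.7%.
- Of expected completers: 230 × 0.9 = 207, and 50 / 207 = 24.2%.
- Controls: 0 / 230 = 0%.
- Section 11.1 also mentions totals of 476 and 500. These give 50 / 238 = 21.0% and 50 / 250 = 20.0%, so the share hardly depends on which total applies.

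**Step 3. What the booking tells someone who knows the rule**
- Under intact 1:1 blinding, P(OPS) = 50%.
- Given a second CT, P(OPS) = 50 / 50 = 100%.
- Given no second CT, P(OPS) = (230 − 50) / (460 − 50) = 180 / 410 = 43.9%. The absence of a scan is only weakly informative.

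**Step 4. Largest effect on a 12-month mean difference.** Let d be the shift in a score caused by knowing the arm. If it applies in full to all 50 and to no control, the arm difference moves by (50 / n) × d:
- n = 230: 0.22d.
- n = 207: 0.24d.

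The documents give no value for d, so the result is left as a multiple. Each assumed point of shift moves the difference by at most 0.22 to 0.24 points.

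**Step 5. If section 11.6 were applied to these patients.** 12-month data gathered after unblinding would be dropped for up to 50 OPS patients. That leaves 230 − 50 = 180 of those randomised, or 207 − 50 = 157 completers. Controls would lose none. Such a loss cannot be squared with intention to treat in 11.2.

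**The case against.** Four points are made on the other side.

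**Order of events.** A reader might infer that the scan reveals the arm before or during assessment. The documents do not say so. Visit 7 lists the CT after PROMs, examination, event recording, x-rays and gait, with only the records review below it. That list is not a sequencing rule, but nothing supports the opposite order either. What stands is that no rule puts the scan last, and a scan would normally be booked before the visit.

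**Patients.** A reader might also infer that patients will know. Section 8.3 requires them to be told what taking part means for them. It does not require disclosure that the second CT is confined to OPS, and the information sheet is not available for review. The patient route is therefore conditional. The assessor route is not conditional on that sheet, because the rule is in the protocol.

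**Existing separation of roles.** Section 8.4 restricts the allocation list to coordinators and operating surgeons and keeps them out of post-operative data. Only they could draw a sample from arm 2, so the staff needed to protect the blind are already in place. What is missing is an instruction on booking and order.

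**Reach.** It is tempting to extend the point to the primary outcome or to the cup-position result. Dislocation and re-operation for it are much less open to expectation than a score. The cup-position objective compares achieved with planned position within the OPS arm, so an unblinded CT reader biases no comparison between arms.

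**Conclusion.** The concern holds as a risk to the 12-month secondary outcomes. The plan sends up to 22% of the OPS arm (24% of expected completers) and no controls for a scan that identifies their arm to anyone who knows the rule, at the visit where the final scores are taken. Nothing in the plan protects the blinding stated in 8.4 and 8.5 for this subset.

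The bound of 0.22d to 0.24d is a worst case. It assumes that all 50 cases are recognised before scoring and that each shifts by the same d. The true effect could be much smaller, or nil if sites happen to scan last and keep the booking from assessors. The 3- and 6-month data are unaffected unless selection is disclosed before those visits.

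Section 11.6 leaves a second problem open. If CT selection counts as unblinding, the consequence is a one-sided loss of 12-month data; if it does not, possibly biased data stay in. The plan does not say which applies. This is a worthwhile and inexpensive correction, and it is not a threat to the primary comparison.

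**What to change.** - **8.4 and 8.6 (Visit 7):** require all 12-month PROMs, Harris hip score, examination and gait data to be completed and entered before the patient or the assessor learns of CT selection. This works whatever the information sheet says.
- **Booking:** have an already unblinded coordinator, who has no role in post-operative data collection, arrange the CT as the last procedure.
- **X-rays:** lock the 12-month leg-length readings before any post-operative CT is opened.
- **8.4 and 8.5:** state that reading of CT cup position is not blinded to arm. This is a wording correction only, since that objective is single-arm.
- **11.6:** state that selection for the CT does not remove a patient's 12-month data from the intention-to-treat analysis.

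**Cost:** a short amendment and a fixed order for Visit 7, with no extra scans or staff. Withholding selection until the assessments are entered makes same-day slots harder to arrange; section 8.6 already allows that CT and gait analysis may not fit on one day at baseline. Some of the 50 may therefore need a separate attendance, for which travel is already reimbursed (8.6, 14.6).
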